5.0 Study Procedures

Note that given the high contagiousness of SARS-CoV-2, the limited supply of personal protective equipment, and risk to coordinators' health, study visits, procedures, and monitoring will be performed in a no-touch mode. This also applies to the consenting process, which will be performed via a consenting mechanism that confirms the identity of the patient, provides access to the consent form, and obtains a signature to complete documentation, without requiring physical proximity of research staff and the study subject.

5.1 Study commencement. After informed consent and enrollment, coordinators will complete the baseline CRF, and initiate study procedures, including randomization (variable permuted block randomization by hospital).

5.2 Study drug. This is an open label, randomized, active comparator trial. Patients who are discharged home will not continue treatment after hospital discharge. If the patient has already received azithromycin or hydroxychloroquine prior to randomization (no more than 2 days), the prior doses will count toward the 5-day total dose. For enrolled patients whose laboratory testing returns negative for SARS-CoV-2, if the clinical team believes that another cause of the patient's presentation is more likely than COVID-19 in light of the negative laboratory testing, the clinical team may stop study drug. Such discontinuation will be recorded. Since the fundamental clinical question is whether to start treatment in patients with suspected or confirmed COVID-19, these patients will remain in the primary analytic cohort.

The trial will be temporarily suspended for enrollment at a given site in the event that no study drug is available at that site.

5.2.1. Hydroxychloroquine. Patients in the hydroxychloroquine arm will receive hydroxychloroquine 400mg po BID x 1 day, then 200mg po BID x 4 days³ (dose reductions for weight < 45kg or GFR<50ml/min). For patients < 45kg, doses will be halved. For patients with GFR<50ml/min, the final dose of hydroxychloroquine will not be administered. The drug dose chosen falls at the lower end of doses proposed in various international trials, but it has proven in vitro efficacy, with a ratio of lung tissue trough concentrations to the EC50 (effective concentration to suppress 50% of viral activity) of >20.³ Given in vitro confirmation of the adequacy of the dose and likely superior safety profile at the lower dose, we chose the total dose of 2.4gm over 5 days.

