5.4.1 Potential risks and risk mitigation. The package insert for hydroxychloroquine lists visual impairment, cardiac impairment, QTc prolongation, worsening of psoriasis or porphyria, proximal myoneuropathy, suicidality, and hypoglycemia. Other reported risks include nausea, diarrhea, vomiting, abdominal pain, headache, dizziness, allergic reactions, rash, low blood counts, seizures, and death. All of these risks are quite rare and where observed are seen after prolonged administration, generally in the range of years. While ocular examinations are recommended after a year (and for acute symptoms), routine ocular examinations have never been recommended for brief duration of therapy. While QTc prolongation has been described, it is generally modest, and routine EKG monitoring is not normally practiced with administration of hydroxychloroquine. In addition, there is some concern that in patients with very low body weight or with low GFR the risk of adverse events may be increased. The potential risks of azithromycin primarily relate to QTc prolongation and *Clostridioides difficile* infection (CDI). Both are clearly described but quite rare with azithromycin.¹⁹ Additional risks include nausea, diarrhea, vomiting, and abdominal pain, allergic reactions, rash, infusion site reaction when given through a vein, abnormal liver function, drug interactions, development of drug-resistant bacteria, heart problems, muscle weakness, cardiac arrest, death. When hydroxychloroquine and azithromycin are co-administered, a modest prolongation in QTc may be observed, which is why we chose the more conservative threshold of 500msec rather than 550msec as an exclusion criterion.

In order to mitigate these risks, we have defined eligibility criteria that exclude patients with elevated risk, keep dosage low, and restrict treatment to just 5 days and avoid outpatient therapy. Patients are monitored within the hospital during treatment. Research coordinators and/or data queries will monitor for adverse events.

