5.4.1.1 Monitoring EKG. An EKG will be performed between 24 and 48 hours after randomization (if no clinical EKG has been performed, then the EKG will be performed as a study procedure). This EKG is performed to determine whether the QTc is prolonged after the loading dose. If the QTc is > 500 ms, study drug will be stopped and an assessment made. If there are no other contributors than study drug to prolonged QTc, study drug will be stopped permanently. If there are contributors to QTc that can be reversed (e.g., electrolytes or other QT-prolonging drugs), these will be reversed at the discretion of the clinical team, with a follow-up EKG performed at the clinical team's discretion. If the QTc is again <500 ms, the study drug will be resumed, with another EKG the day after resumption of study drug. If QTc is again >500 ms, study drug will be permanently discontinued.

5.4.1.2 Daily medication review. For the 5 days of therapy, study personnel and/or clinical pharmacists will review medications being prescribed for patients on study. If a medication is being prescribed that is known to prolong QTc, study personnel and/or clinical pharmacists will contact the prescribing clinician to discuss whether the new medication is necessary and important and to make a clinical determination whether study drug and the new medication should be continued. This review will highlight especially the two classes of medications enumerated in Appendix 5.

5.4.2 Reporting and Regulatory Compliance. All relevant information will be reported in compliance with relevant regulations and Good Clinical Practice. This is not a registrational trial but will be performed under an IND exemption, which was obtained before study launch.

5.4.3 ClinicalTrials.gov registration. An appropriate entry in Clinicaltrials.gov will be created before any patient enrollments occur. Updates to the Clinicaltrials.gov entry will be made in compliance with relevant regulations.

5.4.4 Records retention. Study sites will arrange for the retention of raw data as per institutional protocol but for a minimum of 5 years after receipt of any applicable regulatory notification relevant to this study. All data and

documents will be made available when requested by appropriate authorities. Records will be maintained to verify the existence of each patient in the study, as per standard protocol.

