descriptively by treatment group. If the baseline QTc is available in at least 80% of participants, an analysis of covariance will be performed to compare follow-up QTc between treatment groups with adjustment for baseline QTc. Otherwise, a 2-sample t-test will be used to compare the follow-up QTc levels.

Table 2 Safety outcomes (measured daily for first five days)
Death unrelated to study drug or procedures
Seizure
Receipt of vasopressors
Atrial or ventricular arrhythmia
Cardiomyopathy
cardiac arrest
Hypoxemia requiring supplemental oxygen
ARDS
Mechanical ventilation
ECMO
Elevated LFTs
Pancreatitis
Acute kidney injury
Renal replacement therapy
Symptomatic hypoglycemia
Hematologic or coagulation events
Cytopenias
Severe dermatologic reaction

Nausea/vomiting
Visual changes
C. diff infection

Concomitant medications

The classes of concomitant medications listed in Table 3 were measured at baseline (before randomization) and through day 5 after randomization. Concomitant medications will be descriptively summarized overall and by treatment group. In addition, some patients in the hydroxychloroquine arm received azithromycin either before or in some cases after randomization. The proportion receiving azithromycin was recorded, and in exploratory summaries, safety outcomes will be displayed in that group as well as in the groups who received only azithromycin or only hydroxychloroquine.

Table 3. Concomitant medications
ACE inhibitors
ARBs
NSAIDs
Glucocorticoids
Immune-suppression
Chloroquine
Hydroxychloroquine
Azithromycin
Zinc
Vitamin C

Interim Monitoring.

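### The SAP plans no count of follow-up QTc above 500 ms, the protocol's own action point, and its exposure-group display need not include QTc

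*SAP*

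**What the plan says.** **Action point.** Protocol 5.4.1.1 schedules one EKG at 24-48 h after randomization, to look at QTc once the loading dose has been given. The rule is categorical: "If the QTc is > 500 ms, study drug will be stopped and an assessment made". The stop is permanent if study drug is the only contributor. If another contributor is reversed and QTc falls below 500 ms, drug is resumed and an EKG follows the next day. A second value above 500 ms ends study drug.

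**Analysis.** SAP, Safety reporting, describes follow-up QTc and its change from baseline by treatment group. The formal comparison is an analysis of covariance if baseline QTc is available in at least 80% of participants. "Otherwise, a 2-sample t-test will be used to compare the follow-up QTc levels". Table 2 of the SAP (safety outcomes) includes arrhythmia and cardiac arrest but no QTc item.

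**Exposure groups.** SAP, Concomitant medications, records that some hydroxychloroquine-arm patients also received azithromycin, before or after randomization. In exploratory summaries, "safety outcomes will be displayed in that group as well as in the groups who received only azithromycin or only hydroxychloroquine".

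**Dose.** Protocol 5.2.1 gives "hydroxychloroquine 400mg po BID x 1 day, then 200mg po BID x 4 days" and adds that "we chose the total dose of 2.4gm over 5 days". Where a patient was treated before randomization (no more than 2 days), "the prior doses will count toward the 5-day total dose" (Protocol 5.2).

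**The concern.** The trial manages QTc by a threshold and analyses it as a mean. A mean by arm cannot show how many patients crossed 500 ms, or which drugs they had taken. Protocol 5.4.1 names QTc prolongation as a risk of each drug and adds that "When hydroxychloroquine and azithromycin are co-administered, a modest prolongation in QTc may be observed". Actual exposure is therefore the natural second way to look at these data, and the SAP has already defined the groups. Because QTc is missing from Table 2, nothing commits the analysts to showing it there.

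At stake is the completeness of the safety report. A reader could see two similar mean QTc values and not learn how many patients exceeded the trial's own limit, how many had drug held and resumed, or whether those patients had received both drugs.

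**Working it through.** **1. Where a follow-up QTc above 500 ms would be reported**

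| Course under Protocol 5.4.1.1 | Planned reporting |
|---|---|
| Study drug the only contributor; permanent stop | Adverse event leading to permanent discontinuation (Protocol 7.1; SAP, Safety reporting); counted once per patient, Chi-square or Fisher test |
| Contributor reversed, drug resumed, QTc above 500 ms again; permanent stop | As above |
| Contributor reversed, drug resumed, QTc stays below 500 ms | Not a permanent discontinuation. Reported only if judged serious, or related to study drug or of uncertain relationship (Protocol 7.1, 7.2) |

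In all three rows the value enters the arm mean. Only the third row lacks an assured count. It also arises exactly when another contributor has been found, which makes attribution to study drug less likely.

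**2. Share of the course given at the EKG**

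Total hydroxychloroquine: 2 × 400 + 8 × 200 = 2,400 mg, which reproduces the protocol's 2.4 g. The figures below take the first dose at randomization and exclude a dose falling due exactly at the EKG.

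| Patient | At 24 h | At 48 h |
|---|---|---|
| No prior hydroxychloroquine | 800/2,400 = 33% | 1,200/2,400 = 50% |
| One prior day | 1,200/2,400 = 50% | 1,600/2,400 = 67% |
| Two prior days | 1,600/2,400 = 67% | 2,000/2,400 = 83% |
| GFR < 50 ml/min (last dose omitted) | 800/2,200 = 36% | 1,200/2,200 = 55% |

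Halved doses for low weight leave the shares at 33% and 50%. A first dose given 12 h after randomization lowers the 24 h share to 400/2,400 = 17%. Azithromycin: 500/1,500 = 33% and 750/1,500 = 50%.

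**3. What a count could and could not detect**

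The documents give no QTc mean, SD or event rate. Assume normal QTc, an azithromycin mean of 440-450 ms, an SD of 25-40 ms, a hydroxychloroquine shift of 5-10 ms, and 150 per arm (300/2, with equal allocation and an EKG on everyone). Tests are two-sided at 0.05.

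One case in full (mean 440, SD 30, shift 10):
- Proportions above 500 ms: 1 − Φ(60/30) = 0.023 and 1 − Φ(50/30) = 0.048.
- Expected counts: 150 × 0.023 ≈ 3.4 and 150 × 0.048 ≈ 7.2 patients.
- Means: SE = 30 × √(2/150) = 3.46 ms; 10/3.46 = 2.89; power = Φ(2.89 − 1.96) = 0.82.
- Proportions: SE = √[(0.023 × 0.977 + 0.048 × 0.952)/150] = 0.021; power about 0.22.

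Over the whole grid, the expected numbers above 500 ms are about 1-16 on azithromycin and 2-24 on hydroxychloroquine. Power is 19-93% for the means and 7-31% for the proportion.

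**The case against.** The strongest defence is that most of what matters is already reported, and several stronger readings do fail.

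- **A reader might infer that QTc above 500 ms is never counted.** The documents do not support that. Permanent stops are adverse events with per-patient counts and a test. Protocol 7.1 also collects nonserious events judged related or of uncertain relationship, and Protocol 5.7 (Safety) gives special attention to package-insert events, which by 5.4.1 include QTc prolongation. What stands is that a measured threshold crossing depends on an investigator's judgement, in an open-label trial, whenever drug is resumed.
- **A reader might infer that only means will be shown.** The formal tests use means, but descriptive summaries by arm are also planned and could show the tail. They are not required to.
- **A reader might infer that co-exposed patients are not shown.** Their safety outcomes are, including arrhythmia and cardiac arrest. Only a QTc display in that group is not assured.
- **A reader might infer that the 500 ms stopping value was chosen because of co-administration.** Protocol 5.4.1 gives that reason for the exclusion criterion. Section 5.4.1.1 gives none for the stopping rule.
- **A reader might infer that the EKG timing contradicts the five-day course.** It does not. The protocol says openly that the EKG is a check after loading, and 5.4.1.2 adds daily review of QT-prolonging drugs. There is nothing to reconcile.
- **A reader might infer that a count would detect what the means test misses.** When the whole distribution shifts, the count is the weaker test.

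**Conclusion.** The point holds as a modest reporting gap. No tabulation of follow-up QTc above 500 ms is planned by arm or by actual exposure, although that is the value at which the protocol acts and the SAP confirms that co-exposed patients exist. The patients at risk of going unreported are those whose drug was held, then resumed, and whose event was not judged serious, related or of uncertain relationship.

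The case rests on what a count shows, not on power: with the assumed distributions it would be small and mainly descriptive. The EKG reflects a partial course, 33-50% of the hydroxychloroquine dose without prior use and up to 83% after two prior days. That limits what the QTc results can say, but it is not an error in the protocol. No conclusion is drawn about the clinical stopping rule.

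**What to change.** Change the SAP only:

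1. Add follow-up QTc above 500 ms on the 24-48 h EKG to Table 2, with the planned Chi-square or Fisher comparison. Footnote that it is measured once, unlike the daily items, and that the denominator is patients with an EKG in the window.
2. Show this count and the QTc summary in the three exposure groups already defined. Label the display exploratory, since those groups are not randomized.
3. Report by arm the number with study drug held, resumed and permanently stopped for QTc.
4. If later for-cause EKGs are tabulated, keep them separate and label them descriptive.
5. State beside the results that the EKG reflects a partial course, with the shares above.

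The cost is one table row, one display and a few lines of text, using EKGs already taken. Much of item 3 should be to hand: the SAP's adherence measure (General) treats prolonged QTc as a protocol-specified reason for a missed dose, so those doses have to be identified anyway. The drawback is sparse counts and one more unadjusted p-value, so no gain in power over the means test should be claimed.

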After randomization, adverse events related to protocol procedures or occurring after the patient receives the first dose of study drug must be evaluated by the study investigator. If the adverse event is judged to be reportable, the investigator will report to the DSMB his/her assessment of the potential relatedness of each adverse event to study drug or study procedure. Investigators will assess whether there is a reasonable possibility that the study drug or procedure caused the event, based on the criteria outlined in Appendix 4. Investigators will also consider whether the event is unanticipated or unexplained given the patient's clinical course, previous medical conditions, and concomitant therapies.

Adverse events that will be collected prospectively as part of the study-specific outcome (and thus would not be separately reported as adverse events) are listed in Appendix 4. Study-specific outcomes will be reported as adverse events if they are both serious and Definitely or Possibly Related to study drug.

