7.2 Serious Adverse Events

Serious adverse event collection begins after the patient or LAR has signed informed consent and has received study drug or undergone study procedures. If a patient experiences a serious adverse event after consent, but prior to receiving study drug, the event will NOT be collected unless the investigator feels the event may have been caused by a study procedure.

Investigators must alert the DSMB of any **serious and study drug or study procedure related** adverse event within 24 hours of investigator awareness of the event. Alerts issued via telephone are to be immediately followed with official notification on the adverse event case report form. See Appendix 4 for reporting timelines for serious, unexpected, study related events (SAEs) and serious, unexpected suspected adverse reactions (SUSARs).

As per federal definitions (primarily in 21 CFR 312.32(a)), a **serious** adverse event is any adverse event that results in one of the following outcomes:

- Death
- A life-threatening event, one that places the subject at immediate risk of death (this does not include an event that, had it been more serious, would have placed the subject at immediate risk of death)
- Prolonged inpatient hospitalization or rehospitalization
- Persistent or significant disability/incapacity, indicating a substantial disruption of a person's ability to conduct normal life functions (i.e., the adverse event resulted in a significant, persistent or permanent change, impairment, damage or disruption in the patient's body function/structure, physical activities and/or quality of life).

Important medical events that may not result in death, be life-threatening, or require hospitalization may be considered serious adverse events when, based upon appropriate medical judgment, they may jeopardize the patient and may require medical or surgical intervention to prevent one of the outcomes listed in this definition.

Serious adverse events will be collected during the first five days, regardless of the investigator's opinion of causation. Thereafter, serious adverse events are not required to be reported unless the investigator feels the events were related to study drug or a protocol procedure.

APPENDICES

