Investigators will grade the strength of the relationship of an adverse event to esmolol or study procedures as follows:

- Definitely Related: The event follows: (a) a reasonable, temporal sequence from study drug or a study procedure; and (b) cannot be explained by the known characteristics of the patient’s clinical state or other therapies; and (c) evaluation of the patient’s clinical state indicates to the investigator that the experience is definitely related to study procedures.
- Probably or Possibly Related: The event should be assessed following the same criteria for “Definitely Related”. If in the investigator’s opinion at least one or more of the criteria are not present, then “probably” or “possibly” associated should be selected.
- Probably Not Related: The event occurred while the patient was receiving esmolol or undergoing study procedures but can reasonably be explained by the known characteristics of the patient’s clinical state or other therapies.
- Definitely Not Related: The event is definitely produced by the patient’s clinical state or by other therapies administered to the patient.
- Uncertain Relationship: The event does not meet any of the criteria previously outlined.

[figure not shown]
A4.3. CLINICAL OUTCOMES THAT MAY BE EXEMPT FROM ADVERSE EVENT REPORTING

Study-specific clinical outcomes of COVID-19 or ARDS are exempt from adverse event reporting unless the investigator deems the event to be related to the administration of study drug or the conduct of study

procedures (or of uncertain relationship). The following are examples of events that will be considered study-specific clinical outcomes

- Death (unless Definitely or Probably related to study drug or procedures)
- Respiratory events: Changes in degree of hypoxemia or its treatment
- Cardiovascular events: changes in doses of vasoactive drugs; cardiac arrest; cardiac arrhythmias.
- Organ dysfunction events: changes in the SOFA score or its constituents.
- ICU admission
- Rash
- Hypoglycemia
- Seizure
- Elevations in ALT, AST, lipase, and amylase
- Acute Kidney injury and dialysis
- Cytopenias
- Nausea/vomiting
- Impaired vision
- *C. difficile* infection

A4.4. DECISION TREE FOR REPORTING ADVERSE EVENTS

Adapted from Ranieri VM, Thompson BT, Barie PS et al. Drotrecogin alfa (activated) in adults with septic shock. *N Engl J Med.* 2012 May 31;366 (22):2055-64. Epub 2012 May 22. PubMed PMID: 22616830 with permission of [name].

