discharge. This approach will be used because persisting limitations are unlikely to have resolved and then recurred by 14 days. Similar single imputation rules will be devised for sensitivity analyses of secondary efficacy endpoints consistent with prior practice in the field and will be determined before the given analysis is performed to avoid bias from knowledge of outcomes.

Safety reporting

The HAHPs trial uses the adverse event reporting developed for the PROWESS-SHOCK trial.^{7,8} This approach is based on the high incidence of conditions resulting from the underlying disease that would be classified as adverse events if they occurred in healthy outpatients but are unlikely to be related to the study drug. Instead of being classified as adverse events, such events are monitored as study clinical or safety outcomes (Table 2). The exception to this rule are events which are either serious and study-related or which lead to permanent discontinuation of study drug. Those latter are reported as adverse events and are classified within the MedDRA taxonomy.

For reporting purposes, for each safety outcome or adverse event each patient will be classified as having experienced the outcome at least once (vs. never having experienced the outcome). We will separately provide counts (proportions) of safety outcomes and individual adverse events. In early interim analyses, comparisons of safety outcomes between treatment groups will be viewed as primarily descriptive. However, we will provide nominal p-values to compare adverse events and safety outcomes between groups without multiple comparison adjustment using the Chi square or Fisher exact test as appropriate to provide a crude assessment of the compatibility of observed differences between treatment groups with chance. Isolated p-values which are < 0.05 will be interpreted recognizing that 5% of such p-values will reach this threshold by chance in the absence of an actual effect of the treatment.

QTc was monitored at 24–48h after randomization as a study procedure. QTc monitoring at baseline was not mandatory but was described where it was available. We also described the change between baseline and 24–48h after randomization in QTc. These results will be summarized HAHPs SAP

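### SAP Table 2 counts atrial and ventricular arrhythmia in one row, and no ventricular-only count is planned by randomized arm or by actual exposure

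*SAP*

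**What the plan says.** SAP Table 2, measured daily over the first five days, lists "Atrial or ventricular arrhythmia" as one safety outcome. Under Safety reporting, each patient either had the outcome at least once or never had it. Counts and proportions are given, with an unadjusted nominal chi-square or Fisher p-value between arms.

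Under Concomitant medications, the SAP notes that some hydroxychloroquine-arm patients also received azithromycin. For an exploratory summary it says that "safety outcomes will be displayed in that group as well as in the groups who received only azithromycin or only hydroxychloroquine". That display uses the Table 2 outcomes and does not split the arrhythmia row.

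Arrhythmias are normally kept out of adverse-event reporting. Protocol Appendix 4, A4.3 gives as one class of exempt clinical outcomes "Cardiovascular events: changes in doses of vasoactive drugs; cardiac arrest; cardiac arrhythmias". The SAP states when such an outcome becomes a MedDRA-coded adverse event: "The exception to this rule are events which are either serious and study-related or which lead to permanent discontinuation of study drug".

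Protocol 5.4.1 names QTc prolongation as a risk of hydroxychloroquine and of azithromycin, and says it may be seen when the two are given together.

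**The concern.** Safety is part of the objective in protocol 2.2, and most of the cardiac precautions concern the QT interval: the QTc and long-QT exclusions, the EKG at 24–48 hours and the daily medication review. Ventricular arrhythmia is the rhythm event that QTc prolongation can lead to. Atrial arrhythmia can occur in acutely ill patients whatever drug they receive. In an ever/never row that covers both, a patient with atrial fibrillation and a patient with ventricular tachycardia count the same.

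A reader of the final table could not tell how many patients in each arm, or in the both-drugs group, had a ventricular arrhythmia. A published pooled count cannot be separated later. That matters somewhat here because protocol 5.7 and 5.8 expect the data to feed meta-analyses.

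**Working it through.** **Is a ventricular count planned elsewhere?** These are the routes by which a ventricular arrhythmia could also appear:

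- *MedDRA-coded adverse events (SAP, Safety reporting).* Only events that are serious and study-related, or that permanently stop drug.
- *Return of an exempt outcome to adverse-event reporting.* Protocol 7.1 says "Study-specific outcomes will be reported as adverse events if they are both serious and Definitely or Possibly Related to study drug", so both conditions are needed. A4.3 is wider and also admits events of uncertain relationship.
- *Nonserious events (protocol 7.1).* Collected if related or of uncertain relationship.
- *Serious events (protocol 7.2).* "Serious adverse events will be collected during the first five days", whatever the investigator thinks of causation. No tabulation by rhythm is attached to this.
- *Adverse-event counts (protocol 5.7, Safety).* Special attention to package-insert events; no ventricular item is named.
- *QTc above 500 ms (protocol 5.4.1.1).* Stops drug, permanently in some cases. This acts on the EKG interval and is not a rhythm count.
- *Cardiac arrest row and QTc comparison (SAP).* The first misses ventricular arrhythmia without arrest; the second is a surrogate.

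Together these capture some ventricular events. None counts all of them, and the exposure display covers safety outcomes only, not adverse events.

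**How much does pooling blur?** The documents give no arrhythmia rate and no exposure-group size, so there is no planned figure to reproduce and every rate below is an assumption. The target of 300 patients is from the SAP; 150 per arm is assumed.

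Let v be the ventricular rate and a the atrial rate, with a equal in both arms and the two independent. The pooled rate is 1 − (1 − v)(1 − a). For v = 0.5% vs 2% and a = 5%:

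- lower-risk arm: 1 − 0.995 × 0.95 = 0.05475, and × 150 = 8.2 patients
- higher-risk arm: 1 − 0.98 × 0.95 = 0.069, and × 150 = 10.4 patients
- risk ratio: 0.069 / 0.05475 = 1.26, against 2 / 0.5 = 4.0 in a ventricular row (0.75 vs 3.0 patients)

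At a = 10% and 15% the pooled risk ratio is 1.13 and 1.08.

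The chance of a tie or wrong direction is the probability, from two independent binomials, that the observed proportion in the higher-risk group is no larger than in the lower-risk group. Power is exact for Fisher's test at two-sided 0.05. Pooled ranges cover a = 5%, 10% and 15%.

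| Assumed ventricular rates | Expected ventricular patients | Tie or wrong direction: ventricular row | Tie or wrong direction: pooled row | Power: ventricular row | Power: pooled row |
|---|---|---|---|---|---|
| 0.5% vs 1% | 0.75 vs 1.5 | 45% | 48–49% | <0.01 | 0.03–0.04 |
| 1% vs 2% | 1.5 vs 3.0 | 32% | 41–45% | 0.02 | 0.04 |
| 0.25% vs 1% | 0.4 vs 1.5 | 34% | 44–47% | <0.01 | 0.03–0.04 |
| 0.5% vs 2% | 0.75 vs 3.0 | 18% | 35–41% | 0.04 | 0.04–0.05 |
| 1% vs 4% | 1.5 vs 6.0 | 6% | 20–30% | 0.23 | 0.07–0.11 |

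For the exposure display, assume 0.5% vs 2% and 150 azithromycin-only patients. With 75 both-drugs patients, 75 × 0.02 = 1.5 ventricular events are expected, the chance of none is 0.98^75 = 0.22, and tie or wrong direction is 28% split vs 39–43% pooled. With 38 patients, 0.8 events are expected and the chance of none is 0.98^38 = 0.46. Splitting then gives no advantage on this measure (47% split vs 42% pooled at 5% atrial), because ties are common when counts are near zero.

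**The case against.** The strongest reply is that little follows from this. The SAP treats its safety p-values as crude and the exposure display as exploratory, so the detail of one descriptive row is partly a matter of taste. Nor do the documents suggest a fourfold ventricular contrast between arms: QTc prolongation is a risk of both drugs, and some hydroxychloroquine patients also received azithromycin. At a ratio of 2 the benefit of splitting shrinks, at 0.5% vs 1% to a few percentage points. The other routes narrow the number of events visible only in the pooled row, perhaps to a few patients.

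All of this stands, and it limits the weight of the point. It does not supply the missing count. Absolute ventricular counts are informative even when the arms are similar.

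Two stronger readings are tempting. A reader might infer that ventricular arrhythmias go unreported or that cardiac safety is unmonitored. The documents do not support that: the routes above exist, and Appendix 4 has the DSMB review adverse events and clinical outcomes at interim analyses. A reader might also infer that pooling costs the trial real power to detect a ventricular signal. That needs large assumed contrasts, such as 1% vs 4%, which have no source in the documents; even there the power of a ventricular row is only 0.23.

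**Conclusion.** The point holds as a minor reporting gap. The pooling is a stated rule, and no section of either document plans a ventricular-only count by arm or exposure group. The cost is lost visibility of a few QTc-linked events, not lost power. Under the assumed rates the improvement in showing the right direction ranges from about 3 percentage points (0.5% vs 1%) to about 17–24 (0.5% vs 2%). It rests on 150 per arm, equal and independent atrial rates of 5–15%, and ventricular rates that the documents do not give. The primary analysis, sample size and stopping are unaffected. The case report form is not in the documents, so this concerns planned reporting and does not imply that rhythm type went unrecorded.

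**What to change.** Keep the pooled row and its nominal p-value. Beneath it add two sub-rows, *Ventricular arrhythmia* and *Atrial arrhythmia*, as counts and proportions without p-values, by randomized arm and in the three exposure groups. Use the rhythm type already recorded in the case report form or chart, and count a patient with both in each sub-row.

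The cost is two lines in one table, with no new test and no added multiplicity. The downside is that the counts will be very small and can support description only.
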